procedures based on external tattoos and room lasers. A free- breathing trace of the Calypso transponders will be obtained to allow the patient to settle on the treatment table and to study real-time respiratory traces. The patient will then be asked to perform a therapist-coached modified slow vital capacity maneuver and DIBH maneuver [1] and hold their breath. Patients will have the ability to perform this maneuver with or without biofeedback from digital goggles that are placed over the patient's eyes and display the breathing trace of the Calypso transponders. The use of the digital goggles will be determined by patient preference or at the discretion of the treatment team. This will allow us to investigate whether real-time biofeedback adds to the reproducibility of patients holding their breath. A DIBH cone-beam CT will be acquired in approximately three breath-holds, once a week for standard fractionated RT patients or with each fraction for SBRT patients. After review and approval of the images, the patient will be treated while holding their breath using the DIBH maneuver. In standard fractionated RT patients the radiation treatment will be guided by the external tattoos and daily 2D kV imaging. The Calypso transponder signal will be used to monitor the level of the breath-hold during treatment. The breath-hold level based on the Calypso transponder signal will be verified daily by the 2D imaging and once a week in 3D by the DIBH cone-beam CT. In SBRT patients, the radiation treatment will be guided by the external tattoos and daily DIBH cone-beam CT. The Calypso transponder signal will be used to monitor the level of the breath-hold during treatment. The therapists will monitor the respiratory trace signal from the Calypso transponders throughout the treatment and will initiate the radiation treatment delivery when the patient holds his/her breath within the tolerance level the patient has been assigned to. This will be continued up until the initially planned 30 patients are accrued.. Should the transponder signal indicate that the target has moved outside of the preset tolerance, the therapists will hold further radiation treatment delivery until the patient's breathhold has returned to the desired target range or until the patient's setup has been corrected. In the additional 25 patients planned, the margins will be reduced in a step-wise fashion. The gate will be decreased 1mm per each set of 5 patients until the duty cycle (beam-on time) and number of DIBH attempts are doubled. The gate at which this occurs will be considered the minimum clinically feasible gate

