5. The patient will be remotely asked to repeat the DIBH maneuver and a CBCT will be obtained over several breathholds (exact number depending on the patient's ability to hold their breath) using partial arcs and the assigned breath hold tolerance window.
6. The CBCT images will be evaluated and the patient will be repositioned for a soft tissue match as needed. The soft tissue match will then be evaluated and approved by the treating physician as is our normal clinical process. The isocenter coordinates in Calypso will be changed based on the patient's repositioning shift dictated by the CBCT soft tissue match. No more than 2 CBCTs per treatment will be done for protocol purposes.

The patient will then be remotely asked to reproduce the DIBH maneuver with the tolerance window to which they have been assigned and be treated in DIBH. Number of beam holds, treatment interruptions and total treatment time from first beam-on time to the last beam-off time will be recorded by the therapists. Beacon position during DIBH will be monitored by the therapist to assure that the patient maintains the DIBH position throughout the treatment delivery. If the Calypso beacon signal indicates that the tumor has moved outside of the tolerance window, the radiation beam will be automatically held by the system and resumed when the target is within range.

9.2 For patients undergoing standard fractionated RT the following procedures will be performed:

1. Standard setup procedures based on external tattoos will be performed.
2. The Calypso antenna will be deployed and positioned over the patient's chest. Tracking of the Calypso transponder signal will commence.

Optional: In patients where the Calypso antenna external markers detected by an in-house infrared tracking system can be arranged in such a way that both signals can be obtained

simultaneously (depending on body habitus), a free-breathing trace of the Calypso transponders over 2 minutes in combination with the external marker signal will be obtained . These will be used for future analysis and building of an external/internal respiration model.

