Reproducibility of using internal tumor surrogates (Calypso beacons) during repeated deep inspiration breath hold maneuvers with and without visual biofeedback will be evaluated by posthoc analysis of the Calypso signal traces. The ability to maintain the breathhold to within the tolerance level to which they have been assigned will be assessed. Number of beam holds and treatment interruptions will be recorded as an objective measure of the patient's ability to maintain their breathhold. Whether or not visual biofeedback will aid in the ability to hold their breath reliably and within the target region will be assessed using the number of treatment interruptions. We will also assess differences in duty cycle and number of DIBH attempts with and without visual biofeedback. Differences in the ability of maintaining the DIBH maneuver within the gate with and without visual biofeedback will be measured as duty cycle, a quantifiable measure of how long it takes to deliver a radiation treatment. It is related to how well patients can hold their breath and the tumor in the target position. Each patient will have the goggles 50% of the treatments and without goggles the other 50% of the time. Wilcoxon rank sum tests will be done to compare the duty cycle.

The residual intrafraction motion and drift during DIBH will be determined based on the Calypso signal traces which may provide critical insight into the ability to immobilize the tumor by DIBH. Beacon position stability will be determined on acquired cone-beam CTs by measuring the distance of the beacons to the center of the gross target volume {GTV} as well as the distance of the beacons to each other. Improvement of normal tissue dosimetry based on Calypso-guided DIBH will be determined from the treatment plans developed on the free-breathing and DIBH simulation CT scans. Specific dosimetric parameters will include the chest wall V30, total lung V20, mean lung dose, lung toxicity model metrics (Lyman model NTCP and parallel model fraction damaged (fdam)), mean and maximum esophageal dose, and maximum spinal cord dose.

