To determine the minimum clinically feasible gate margins we will decrease the gate in a step-wise progression as far as a minimum of 2 mm. The gate will be reduced from +/- 5mm by 1mm for every 5 patients treated. Halving of the duty cycle will be considered the minimum gate that is clinically feasible. Once the minimum gate is determined, the remaining patients will be treated at +1mm from this value.

In the additional 10 conventionally fractionated patients, tumor shrinkage will be summarized as relative shrinkage in a percentage. Beacon position and centroid are 3D coordinates that will be determined as a distance from a landmark such as a bone or the carina.

Lung volume preservation will be assessed on wide field of view cone-beam CTs and compared intra- and interfraction within each patient to check for reproducibility or variability of lung volumes across multiple DIBH maneuvers.

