For the 1st secondary objective, we will compare the visual vs no visual biofeedback treatments (for patients who agree to use the digital goggles) by the number of treatment interruptions. We expect that there will be fewer treatment interruptions when using biofeedback. To this end Wilcoxon signed-rank tests will be conducted based on the patients who can successfully be treated.

For the 2nd secondary objective, we will assess differences in the ability of maintaining the DIBH maneuver within the fate with and without visual biofeedback. Such differences will be measured as duty cycle, and will be compared using Wilcoxon signed-rank tests based on the patients who can successfully be treated.

For the 3rd secondary objective, the residual intrafraction tumor motion (surrogated by Calypso) will be measured in all 3 dimensions and the euclidean distance will be calculated, which will then be correlated with the normal tissue dosimetry (see end of Section 12.0). Patients will receive multiple fractions and thus multiple measurements of such distance will be obtained from the same patients.

These repeated measures will be averaged for each patient and the correlation will be examined by simple linear regression. If such continuous data are skewed, we may either use an appropriate monotone transformation, or examine the nonparametric correlation coefficient (such as Spearman rank correlation coefficient) between the tumor motion and the normal tissue dosimetry instead.

For the 4th secondary objective, the potential increase in dose escalation and decrease in margins made possible by Calypso- guided DIBH, as contrasted to those obtained from the 40 CT scan, will be formulated as pair data from each patient and tested by using Wilcoxon signed-rank tests. Dosimetric parameters listed at the end of Section 12.0 will be used again for such analysis.

The 5th secondary objective does not require statistical analysis. See Section 12.0 for details.

For the 6th secondary objective, tumor shrinkage, beacon position and centroid changes in conventionally fractionated patients (totally 10), all measured as continuous variables, will be summarized descriptively.

For the 7th secondary objective, intra- and inter-fraction variation in lung volume preservation of multiple DIBH maneuvers will be recorded within each patient and summarized descriptively.

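### The third-objective regression of dosimetry on residual motion has no term for the assigned gate, and the plan does not say whether motion is measured inside the gate or over the whole breath-hold

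*Combined protocol and SAP*

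**What the plan says.** Section 14.0 states that residual intrafraction motion, with the Calypso signal as surrogate, "will be measured in all 3 dimensions and the euclidean distance will be calculated", and is then related to the normal-tissue dosimetry listed in Section 12.0. On the repeated distances it adds: "These repeated measures will be averaged for each patient and the correlation will be examined by simple linear regression". If the data are skewed, a transformation or a rank correlation may be used instead. Neither version contains the assigned gate as a covariate or stratum.

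The gate is varied on purpose. Section 12.0 says: "The gate will be reduced from +/- 5mm by 1mm for every 5 patients treated", "as far as a minimum of 2 mm", and then: "Once the minimum gate is determined, the remaining patients will be treated at +1mm from this value". Section 4.1 describes the same steps. Assignment follows enrolment order, since the study is not randomized (Section 15.2). During delivery, if the beacon signal leaves the assigned window, "the radiation beam will be automatically held by the system and resumed when the target is within range" (Section 9.1, with the same rule in 9.2).

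Section 14.0 does analyse the two patient sets separately, but that sentence is written for the primary objective. Nothing similar appears for the third secondary objective.

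**The concern.** The gate acts directly on motion during delivery. If the distances come only from in-gate samples, a patient given a narrower gate shows less motion by construction. Measuring residual motion is part of the third objective (Section 2.0). A single pooled figure would then partly reflect the number of patients at each gate, and could be misread as what breath-hold achieves by itself. In the regression, gate-driven variation in the predictor blurs any real relation. If dosimetry also differs by gate, it can produce a relation that is not there.

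There are two possible routes from gate to dosimetry. Section 1.0 says: "In the additional 25 patients planned, the margins will be reduced in a step-wise fashion". If that means planning margins, dosimetry would improve as the gate narrows. Separately, Section 4.1 adds at least 10 conventionally fractionated patients to the extension, so the case mix, and with it lung, esophageal and cord dose, may differ between the wide-gate and narrow-gate patients.

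**Working it through.** The plan gives no SD, expected correlation, alpha or power for this objective, so there is no figure to reproduce. The check is a model with stated assumptions.

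**Inputs from the documents.** 55 patients (30 + 25, Section 14.0); gate steps, 2 mm floor and the +1 mm rule (Section 12.0); beam hold outside the window (Sections 9.1 and 9.2).

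**Assumptions.**
- Motion on each axis is normal with mean 0 and a patient-specific SD, lognormal between patients (log-SD 0.35).
- Median per-axis SD is 1.4 to 2 mm, with 1 and 3 mm also tried. The only related figure in the documents is 0.14 cm (Section 3.2), from spirometry-monitored breath-hold with the diaphragm as surrogate, so it is a rough anchor.
- Gate layout is 30 patients at 5 mm, 5 at 4, 5 at 3, 5 at 2, then 10 at 3 (minimum + 1 mm).
- Dosimetry = b x gate + noise with SD 1, and no true effect of motion. The slope b is in residual SDs per mm of gate.

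**Step 1: effect of the gate on in-gate motion.** Mean of sqrt(x² + y² + z²), given that each axis lies within the gate:

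| Per-axis SD | 5 mm | 4 mm | 3 mm | 2 mm | Fall, 5 to 2 mm |
|---|---|---|---|---|---|
| 1 mm | 1.59 | 1.60 | 1.58 | 1.42 | (1.59 - 1.42)/1.59 = 11% |
| 1.4 mm | 2.23 | 2.20 | 2.06 | 1.65 | (2.23 - 1.65)/2.23 = 26% |
| 2 mm | 3.08 | 2.86 | 2.44 | 1.78 | (3.08 - 1.78)/3.08 = 42% |

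**Step 2: the pooled mean as a mixture.** At SD 2 mm the layout above gives (30 x 3.08 + 5 x 2.86 + 15 x 2.44 + 5 x 1.78)/55 = 152.2/55 = 2.77 mm. If the minimum gate were 3 mm, with the last 15 patients at 4 mm, it would be (30 x 3.08 + 20 x 2.86 + 5 x 2.44)/55 = 161.8/55 = 2.94 mm. The patients' own motion is identical in both cases.

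**Step 3: false positives in the regression.** Two-sided 5% test of motion against dosimetry, in-gate motion, n = 55, gate reaching 2 mm:

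| Gate slope b | SD 1.4 mm, no gate term | SD 2 mm, no gate term | Gate as a factor |
|---|---|---|---|
| 0 | about 5% | 5% | about 5% |
| 0.1 | 6% | 7% | about 5% |
| 0.25 | about 10% | about 20% | about 5% |
| 0.5 | about 20% | about 55-60% | about 5% |

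Over the 3 mm from the widest to the narrowest gate, b = 0.25 is a difference of 0.75 residual SD and b = 0.5 is 1.5 SD. At b = 0.5 the rate without a gate term runs from 7% (median SD 1 mm) to 90% (3 mm).

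**Step 4: variations.**
- Whole breath-hold trace: no truncation, and false positives stay near 5% at every b.
- Reduction ends at a 3 mm minimum: 11% at SD 2 mm and b = 0.5. At a 4 mm minimum: 5%.
- Second set alone (n = 25), SD 2 mm: 6%, 8% and 17% at b = 0.1, 0.25 and 0.5.

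**Step 5: power when dosimetry does not track the gate.** For one assumed true relation, in-gate motion and n = 55, adding the gate raised power from 77% to 82% at SD 1.4 mm and from 61% to 80% at SD 2 mm. The levels depend on the assumed strength of the relation.

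**The case against.** A reader might infer that gate assignment alone manufactures a motion-dosimetry correlation. It does not: with b = 0 the false-positive rate stays at about 5%. A link from gate to dosimetry is also needed, and the text for one is weak. In Section 1.0 the sentence on margins is followed at once by one on decreasing the gate, the protocol elsewhere speaks of a gate margin when it means the gate, and Section 9.0 describes the same step as reducing the window. Sections 4.1 and 4.2 say prescription and planning are unaffected by the study, and Section 12.0 takes dosimetry from plans on the simulation scans, not from gated delivery. The fractionation route is possible but unquantified.

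Truncation is also not stated. Section 12.0 says: "The residual intrafraction motion and drift during DIBH will be determined based on the Calypso signal traces", with no restriction to in-gate samples. Section 9.0 lets therapists treat at the best achievable level after three failed attempts, so the gate is not an absolute cut-off. Pooling across gate widths is inferred from silence. Finally, decisions on margins do not rest on this regression: the fourth objective uses paired tests, the fifth uses the duty cycle, and the objective is exploratory with no decision rule.

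All of this stands and limits the claim. It leaves in place that the motion window is undefined, that the model has no gate term, and that in-gate motion would be gate-dependent whatever happens to dosimetry.

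**Conclusion.** The point holds in limited form. The planned analysis omits a design variable that, if motion is measured in-gate, lowers the predictor by about 26% to 42% across the range of gate widths (assumed per-axis SD 1.4 to 2 mm). That makes a pooled motion figure depend on the allocation of patients to gate widths and costs power in the regression. Spurious correlation is conditional: it requires in-gate motion, dosimetry that tracks the gate, and a gate that gets well below 5 mm. With all three, false positives are roughly 10-20% at 0.25 SD per mm and 20-60% at 0.5 SD per mm. Both slopes are assumptions, and the documents do not establish that any such slope exists. The matter concerns one exploratory secondary objective and leaves the primary feasibility analysis untouched.

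**What to change.** In Section 14.0, third secondary objective:

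1. State whether residual motion is computed from in-gate samples or from the full breath-hold trace, and preferably report both.
2. Report residual motion by assigned gate as well as overall.
3. Add assigned gate to the regression as a factor, or stratify the rank correlation by gate.
4. Reconcile Section 1.0 with Sections 4.1 and 4.2 on whether planning margins follow the gate.

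With four gate widths the factor uses up to three degrees of freedom out of about 55 patients, plus one table split. The traces are already recorded and each patient's gate is known. If the full trace is used, the term costs almost nothing; if motion is in-gate, it protects the error rate or recovers power.

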2.0 OBJECTIVES AND SCIENTIFIC AIMS

Primary objectives:

- To evaluate the feasibility of using internal tumor surrogates (Calypso beacons) during repeated deep inspiration breath hold maneuvers for DIBH radiation treatments.

Secondary objectives:

- To compare the reproducibility with visual versus without visual biofeedback.
- To assess differences in the ability of maintaining the DIBH maneuver within the gate with and without visual biofeedback
- To measure the residual intrafraction tumor motion and associated improvement in normal tissue dosimetry during DIBH based on the Calypso lung transponder signal as a surrogate
- To measure the increase in dose escalation and the potential for decreasing margins made possible by Calypso-guided DIBH
- To determine the minimum clinically feasible gate margin for radiation
- To assess tumor shrinkage, beacon position and centroid changes in conventionally fractionated patients
- To assess intra- and inter-fraction variation in lung volume preservation of multiple DIBH maneuvers

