3.2 Preliminary Data

DIBH has been previously explored using coached breath-hold monitored by spirometry [28, 49] and radiographic imaging and using spirometry plus the Elekta "ABC device" together with radiographic imaging[21][18, 27]. An initial series of 5 patients at MSKCC who underwent CT scans under 4 different respiration conditions including DIBH showed that DIBH can reduce the volume of lung receiving more than 25 Gy by 30% compared to free-breathing radiation plans. Patients were able to comfortably hold their breath for 12 -16 seconds and perform 10-13 breath-holds in a single session.[28]

We then showed that coached DIBH with spirometer monitoring decreased estimated normal tissue complication probabilities while allowing for increased tumor doses.[1] Patients were initially maintained at quiet tidal breathing, followed by a deep inspiration, a deep expiration, a second deep inspiration, and breath-hold in deep inspiration (DIBH). Simulation, verification and radiation treatments took place during this last phase of DIBH. Seven patients received a total of 164 treatment sessions with excellent tolerability. None of the seven patients needed to discontinue treatment or resume the free-breathing backup method due to fatigue or inability to perform the DIBH maneuver. On average, the radiation dose could be increased from 69.4 Gy to 87.9 Gy without increasing the risk of toxicity by using DIBH.

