The radiation treatment for patients on this study will be performed according to routine procedures using standard equipment, techniques and treatment planning procedures. The radiation dose prescription criteria will not be changed based on the DIBH maneuver or Calypso transponder implantation on this study. Patients will be followed as per our institutional standard at approximately 3, 6, 9 and 12 months after radiation treatments. Following completion of study participation, patients will be followed as per our institutional standard. They will be evaluated for any potentially transponder-related toxicity. Any toxicities will be carefully evaluated case by case according to the Common Terminology Criteria for Adverse Events (CTCAE) v4.0.

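### The fourth secondary objective promises a gain in achievable dose and a margin reduction, but the plan names only normal-tissue metrics and defines neither a tumor-dose endpoint nor a margin endpoint

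*Combined protocol and SAP*

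**What the plan says.** Section 2.0 sets the aim as "To measure the increase in dose escalation and the potential for decreasing margins made possible by Calypso-guided DIBH", and Section 12.0 repeats it. Sections 1.0 and 4.1 list dose escalation separately from the reduction in dose to normal organs, so the protocol itself treats these as two results.

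Section 14.0 handles this objective in two sentences. The first says that the escalation and margin gains, relative to the 4D CT, "will be formulated as pair data from each patient and tested by using Wilcoxon signed-rank tests". The second supplies the variables: "Dosimetric parameters listed at the end of Section 12.0 will be used again for such analysis".

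In Section 12.0 that list begins "Specific dosimetric parameters will include the chest wall V30, total lung V20, mean lung dose, lung toxicity model metrics" (the two model metrics are the Lyman NTCP and the parallel-model fraction damaged, fdam) and ends "mean and maximum esophageal dose, and maximum spinal cord dose". The sentence that introduces it concerns organ sparing: "Improvement of normal tissue dosimetry based on Calypso-guided DIBH will be determined from the treatment plans developed on the free-breathing and DIBH simulation CT scans".

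Section 9.0 provides two plans per patient, one free-breathing and one DIBH. On prescribing, Section 4.1 states: "The radiation dose prescription criteria will not be changed based on the DIBH maneuver". Section 4.2 adds that dose guidelines and the planning process stay as they are.

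**The concern.** A lower lung V20 or mean lung dose under DIBH shows that lung is spared. It does not show how far the tumor dose could rise, because that depends on whichever constraint is reached first in that patient, and the limiting organ may differ between patients or between one patient's two plans. Section 3.1 itself names both lung and spinal cord as organs whose constraints prevent the optimal prescription. Nor does the list say how far a margin could shrink.

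At stake is the meaning of the reported result. With nothing else defined, a significant fall in a lung metric could be written up as the escalation result even in patients where cord or esophagus leaves little room. A reader could not recover the intended quantity from eight separate tests.

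**Working it through.** The documents give no effect size, power or significance level for this objective, so there is no stated figure to reproduce. The check is of definitions, followed by an illustration.

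**1. What each listed variable measures**

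| Section 12.0 metric | Tissue | Tumor dose? | Margin? |
|---|---|---|---|
| V30 | chest wall | no | no |
| V20 | lung | no | no |
| mean dose | lung | no | no |
| NTCP (Lyman) | lung | no | no |
| fdam (parallel model) | lung | no | no |
| mean dose | esophagus | no | no |
| maximum dose | esophagus | no | no |
| maximum dose | spinal cord | no | no |

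Of the eight, none is a tumor dose and none is a margin.

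**2. Is a conversion given elsewhere?** Sections 4, 9, 12 and 14 contain no rule that turns these metrics into an achievable dose: no limiting constraints, no scaling rule, and no third plan at escalated dose or reduced margin. Two distances in mm do appear. Residual motion belongs to the third objective and is only correlated with normal-tissue dosimetry. The beam tolerance window belongs to the fifth objective, for which Section 14.0 says no statistical analysis is needed. Neither is linked to the fourth objective.

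**3. Why the listed metrics fix no single escalation figure.** Two assumptions here are not in the documents: organ dose scales in proportion to prescribed dose, and the free-breathing plan sits exactly at its limit. If the limiting metric falls by a fraction r under DIBH, the dose that brings it back to the limit is

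achievable dose = D / (1 − r).

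Take D = 60 Gy, the Section 3.1 figure for fractionated treatment of locally advanced disease.

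| r | 60 / (1 − r) | gain |
|---|---|---|
| 5% | 63.2 Gy | 3.2 Gy |
| 10% | 66.7 Gy | 6.7 Gy |
| 20% | 75.0 Gy | 15.0 Gy |
| 30% | 85.7 Gy | 25.7 Gy |

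A patient whose lung falls by 20%, esophagus by 10% and cord by 5% therefore gains 15.0, 6.7 or 3.2 Gy according to which organ limits. The metric differences are identical in all three cases.

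The starting distance from the limit matters too. If lung limits and the free-breathing plan is at 90% of its limit, the same 20% fall takes the achievable dose from 60/0.9 = 66.7 Gy to 60/(0.9 × 0.8) = 83.3 Gy. The gain is then 16.7 Gy, against 15.0 Gy when the plan starts at the limit. A test on the metric difference alone does not see this.

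**4. What the missing endpoint looks like.** Section 3.2 reports one from an earlier series of seven patients: "On average, the radiation dose could be increased from 69.4 Gy to 87.9 Gy without increasing the risk of toxicity by using DIBH". That is 87.9 − 69.4 = 18.5 Gy, or 18.5/69.4 = 26.7%. The present plan defines no equivalent.

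**The case against.** The best defence is that Section 14.0 does name escalation and margin as the paired quantities, so the Section 12.0 list may be meant as input to an equal-risk calculation. NTCP and fdam would suit that purpose, and the list is worded as inclusive. This reading is fair. It means the fault is an undefined endpoint; the text does not prove that organ sparing was meant to replace escalation. It does not supply the limits, the scaling rule or the margin variable.

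It can also be said that cord and esophagus are in the same list, so a limiting organ would not go unseen. That is true across the group. But separate tests do not combine the organs within a patient, and that is where the limit acts.

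Three stronger readings are tempting, and the documents do not support them.

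- *The analysis gives nothing in Gy or mm.* Mean lung, esophageal and cord doses are in Gy, and residual motion and the tolerance window are in mm. What is missing is an achievable tumor dose in Gy and a margin in mm.
- *Both plans carry the same prescribed dose.* The protocol says prescription criteria are unchanged. Equal dose is a reasonable inference but is not stated, and Section 3.1 expects DIBH to let more patients reach the intended 60 Gy.
- *The trial loses an 18.5 Gy result.* That figure comes from a spirometer-monitored series. It shows the form of the endpoint and measures no error here.

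Finally, this is an exploratory secondary objective on which no treatment decision rests. That limits the importance of the point but does not answer it.

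**Conclusion.** The point stands as a definitional gap in one secondary objective. Following Section 14.0 as written would describe organ sparing and leave both the escalation gain and the margin reduction unmeasured.

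The table and the search of the sections rest on the documents alone. The 3.2 to 15.0 Gy spread is an illustration that depends on linear scaling, a free-breathing plan at its limit and assumed organ reductions; it is not a forecast for this trial. No corresponding margin figure can be calculated, because no margin variable is given. Correcting this is a worthwhile, inexpensive improvement, and the primary feasibility conclusion does not depend on it.

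**What to change.** Amend the fourth-objective text in Section 14.0. This is calculation only and changes no prescription.

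- **Escalation endpoint.** For each patient and each of the two existing plans, calculate the dose at which the first of the normal-tissue limits already used in planning would be reached. The documents do not list those limits, so write the list down before analysis. State the linear-scaling assumption. Mean and maximum doses scale directly; V20, V30, NTCP and fdam should be re-evaluated on the scaled dose distribution.
- **Analysis.** Keep the Wilcoxon signed-rank test, applied to the paired difference in that dose, and report the difference with an interval and the limiting organ in each plan. Report SBRT and standard fractionation separately, since an SBRT plan may be far from any limit.
- **Margin endpoint.** Report the paired difference in mm between beacon motion amplitude on the 4D CT and residual motion in DIBH. Section 9.0 already has the beacons contoured on every 4D CT phase, and Section 12.0 already takes residual motion from the traces. Label this as the motion component of the margin only, because Section 3.1 describes a further allowance for positioning. Report it by assigned tolerance window, because the window truncates motion while the beam is on and is narrowed across cohorts.
- **Existing metrics.** Keep the Section 12.0 list as supporting organ-sparing results, and do not describe them as dose escalation.

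The cost is revised wording and some physics time to rescale plans already made. The scaling assumption is the main weakness and should be reported with the result. No new scan, patient or treatment is needed.
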